2. SAE
3. Grade 3 or 4 AE

The time to this composite endpoint will be defined as the elapsed time (in days) from baseline to the earliest date of any of the events. Any subjects that are lost to follow-up or terminated early prior to experiencing any of the events will be censored at the day of their last observed assessment. Subjects who complete follow-up but do not experience any of the events will be censored at the Day 29 visit.

4. INVESTIGATIONAL PLAN

4.1. Overall Study Design and Plan

ACTT-2 will evaluate the combination of baricitinib and remdesivir compared to remdesivir alone. Subjects will be assessed daily while hospitalized. If the subjects are discharged from the hospital, they will have a study visit at Days 15, 22, and 29. For discharged subjects, it is preferred that the Day 15 and 29 visits are in person to obtain safety laboratory tests and OP swab and blood (serum only) samples for secondary research as well as clinical outcome data. However, infection control or other restrictions may limit the ability of the subject to return to the clinic. In this case, these visits may be conducted by phone, and only clinical data will be obtained. The Day 22 visit does not have laboratory tests or collection of samples and is conducted by phone.

4.2. Selection of Study Population

Male and non-pregnant female adults ≥ 18 years of age or older with COVID-19 and who meet all eligibility criteria will be enrolled at up to approximately 100 clinical trial sites globally. The target population should reflect the community at large.

See Section 5.1 and 5.2 of Appendix B of the study protocol for the full list of inclusion and exclusion criteria.

4.2.1. Treatments Administered

All subjects will receive remdesivir as a 200 mg intravenous (IV) loading dose on Day 1, followed by a 100 mg once-daily IV maintenance dose for the duration of the hospitalization up to a 10-day total course.

For the baricitinib component, subjects will receive either active product or placebo as follows:

- Baricitinib will be administered as a 4 mg orally (po) (two 2mg tablets) or crushed for NG tube, daily for the duration of the hospitalization up to a 14-day total course.
- A placebo will be given as two tablets po or crushed for NG tube, daily for the duration of the hospitalization up to a 14-day total course.

4.2.2. Identity of Investigational Product(s)

See Section 6.1.1 of Appendix B of the study protocol.

4.2.3. Method of Assigning Subjects to Treatment Groups (Randomization)

Enrollment and randomization of subjects is done online using the enrollment module of Advantage eClinical[®].

Eligible subjects will be randomized and assigned in a 1:1 ratio to either baricitinib + remdesivir or remdesivir, with stratification by site and disease severity by ordinal scale (Moderate disease [4 or 5 on the ordinal scale] or Severe disease [6 or 7 on the ordinal scale]). The randomization is based on a variable blocked scheme to provide an approximately balanced allocation to the treatment groups during the study. If arms are added or removed later in the study, randomization will continue in an equal allocation manner.

4.2.4. Selection of Doses in the Study

The dose of remdesivir used in this study will be the same dose that has been used in the human Ebola clinical trials.

4.2.5. Selection and Timing of Dose for Each Subject

See Sections 6.1.2 through 6.1.5 of Appendix B of the study protocol.

4.2.6. Blinding

As both arms are receiving remdesivir, the remdesivir product is not blinded and study infusions can be labeled accordingly.

The baricitinib/placebo component is blinded. Baricitinib and placebo tablets are identical in appearance.

Unblinding of the study will occur after all subjects enrolled have reached the end of study, and these visits are monitored and data is cleaned, or if the DSMB recommends unblinding.

If AEs occur and investigators are concerned about the treatment allocation, the treatment can be discontinued. If a Serious Adverse Event occurs, that is thought to be related to the study drug, and the treating clinician believes that knowledge of the treatment arm may change the therapy provided to the patient, the individual subject can be unblinded. The procedure for unblinding will be further detailed in the Manual of Procedures (MOP).

4.2.7. Prior and Concomitant Therapy

See Section 6.5.1 of Appendix B of the study protocol for permitted concomitant therapy and procedures. See Section 6.5.2 of Appendix B of the study protocol for prohibited concomitant therapies.

4.2.8. Treatment Compliance

See Section 6.1.4 of Appendix B of the study protocol for details on dose modifications.

Each dose of study product will be administered by a member of the clinical research team who is qualified and licensed to administer the study product. Administration and date, and time, will be entered into the case report form (CRF).

4.3. Efficacy and Safety Variables

For each study day while the patient is hospitalized, the clinical status will be recorded on an 8-point ordinal scale as follows:

- Day 1 – The clinical assessment at the time of randomization.
- Day 2 + - The most severe assessment occurring from midnight to midnight (00:00 to 23:59) of the prior day (e.g., the value recorded on Day 3 will be the most severe outcome that occurred on Day 2).

where the clinical status scale is defined as follows:

- 8. Death;

7. Hospitalized, on invasive mechanical ventilation or ECMO;
6. Hospitalized, on non-invasive ventilation or high flow oxygen devices;
5. Hospitalized, requiring supplemental oxygen;
4. Hospitalized, not requiring supplemental oxygen- requiring ongoing medical care (COVID-19 related or otherwise);
3. Hospitalized, not requiring supplemental oxygen - no longer requires ongoing medical care;
2. Not hospitalized, limitation on activities;
1. Not hospitalized, no limitations on activities

A modified version of the ordinal scale will be used in sensitivity analyses of the primary and secondary outcomes. The modified scale will be as follows:

8. Death;
7. Hospitalized, on invasive mechanical ventilation or ECMO;
6. Hospitalized, on non-invasive ventilation or high flow oxygen devices;
5. Hospitalized, requiring supplemental oxygen;
4. Hospitalized, not requiring supplemental oxygen- requiring ongoing medical care (COVID-19 related or otherwise);
3. Not hospitalized, limitation on activities;
2. Hospitalized, not requiring supplemental oxygen - no longer requires ongoing medical care; or Not hospitalized, no limitations on activities.

That is, category 1 and 3 of the original scale will be combined into the lowest category.

NEWS has demonstrated an ability to discriminate subjects at risk of poor outcomes. This score is based on 7 clinical parameters (see Section 8.1.2.3 in Appendix B of the study protocol). This should be evaluated at the first assessment of a given study day and prior to administration of study product. The 7 parameters can be obtained from the hospital chart using the last measurement prior to the time of assessment and a numeric score given for each parameter (e.g., a RR of 9 is one point, oxygen saturation of 92 is two points). This is recorded for the day obtained. i.e., on Day N, the Day N score is obtained and recorded as the Day N score.

Oxygenation, Non-invasive ventilation/high flow oxygen, Invasive Mechanical Ventilation / extracorporeal membrane oxygenation (ECMO), hospitalization and mortality will be assessed using results of the 8-point ordinal scale and post discharge eCRF questions.

Safety will be assessed by the following:

- Cumulative incidence of serious adverse events (SAEs) through 28 days of follow-up.
- Cumulative incidence of Grade 3 and 4 AEs.
- Discontinuation or temporary suspension of study product administration (for any reason)

- Changes in white cell count, absolute neutrophil count, hemoglobin, platelets, creatinine, glucose, total bilirubin, ALT, AST, and INR, d-dimer, C-reactive protein over time.

Clinical labs will be drawn on Days 1, 3, 5, 8, 11 and on Day 15 and 29 if the subject is able to return to the clinic or is still hospitalized.

Virologic efficacy is an exploratory endpoint and will be assessed by the following:

- Qualitative and quantitative PCR for SARS-CoV-2 in OP swab on Days 1; 3, 5, 8, 11 (while hospitalized); and Day 15 and 29 (if able to return to clinic or still hospitalized).
- Qualitative and quantitative PCR for SARS-CoV-2 in blood on Days 1; 3, 5, 8, 11 (while hospitalized).

To assess the impact of baricitinib on serum cytokine levels, blood samples will be assessed using a multiplex assay that is less sensitive to variability in sample integrity due to sample processing limitations during the pandemic. Cytokines to be tested may include (but not be limited to) IL-2, IL-19, IL-4, IL-10, IL-8, G-CSF, GM-CSF, MCP-1, MIP1 α , IL-7, IL-13, IL-31, IL-15, IL-6, IFN α , IFN γ and TNF α . The list of cytokines tested is subject to change as new information about the pro-inflammatory state of COVID-19 is known. Given the challenges of obtaining samples and evolving knowledge about COVID-19, these will be considered exploratory endpoints. The description of the final methodology utilized, and the assay performance characteristics will be included in the final study report.

The schedule of study procedures is provided in Section 1.2 of Appendix B of the study protocol.

5. SAMPLE SIZE CONSIDERATIONS

Sample Size for Primary Analysis

The log-rank test will be used to compare treatment arms with respect to time to recovery. For the log-rank test, the two key determinants of power are the total number of events (i.e., recoveries) E and the treatment-to-control ratio of the rate of recovery. The number of events required for power $1 - \beta$ to detect a recovery rate ratio of θ using a two-tailed test at $\alpha=0.05$ is approximately

$$E = \frac{4(1.96 + z_{\beta})^2}{\{\ln(\theta)\}^2},$$

where z_{β} is the $100(1 - \beta)$ th percentile of the standard normal distribution.

The force of recovery (sometimes loosely referred to as the “recovery ratio”) is the analogue of the hazard ratio and the term “recovery rate ratio” is the analogue of the hazard ratio in this setting. A recovery rate ratio of 1.31 was reported in Cao, Wang, Wen et al. (2020) for a lopinavir/ritonavir trial that used time to improvement by 2 categories as primary endpoint. A preliminary review of data from ACTT-1 demonstrated a recovery rate ratio 1.312. It is unlikely the second component of treatment will have a similar effect size. Therefore, a recovery ratio of 1.25 is assumed for this trial. A total of 723 recoveries are needed for a recovery ratio of 1.25 with 85% power. The study will accrue until approximately 723 recoveries have been achieved. The date of study closure will be estimated based on enrollment rate and recovery/enrollment percentages. If approximately 70% of participants recover, the total sample size will be 1032.

See Section 9.2 of Appendix B of the study protocol for discussions on the sample size calculations for the key secondary outcome.

6. GENERAL STATISTICAL CONSIDERATIONS

6.1. General Principles

This is a double-blind, placebo controlled randomized trial with a two-sided type I error rate of 0.05. Secondary hypotheses have been ordered according to relative importance. These will be described according to the appropriate summary statistics, e.g.

- Percentages/proportions/odds ratios for categorical data. For tabular summaries of percentages/proportions, the denominator (e.g. number of subjects with non-missing data) will be displayed.
- Means, median, and range for continuous data, median for time-to-event data.

Confidence intervals will be generated; for the primary analysis, the confidence level will take into account the group-sequential design of the trial (see Section 6.6 and Section 8.1) whereas 95% confidence intervals will be generated for secondary and exploratory outcomes. For hazard ratio and odds ratio estimates, Wald confidence intervals will be used. For other efficacy outcomes, Wilson or Score confidence intervals will be used. For safety outcomes, exact (e.g. Clopper-Pearson) confidence intervals will be used.

When calculating treatment effects (e.g. differences, hazard ratios, odds ratios) and when using treatment arm as a covariate in regression modeling, the remdesivir+placebo arm will be used as the reference group. For regression modeling that uses strata variables defined in Section 6.4, the first stratum listed for each variable in that section will be used as the reference group.

For the final time-to-event analyses, the following SAS pseudocode will be used to perform stratified analyses to generate stratum-specific median time to event estimates and confidence intervals, stratum-specific Kaplan-Meier curves, and to perform the log-rank test. For any unstratified analyses, code can be used after the removal of the `strata ... ;` line.

```
proc lifetest data=dataset plots=(s);
  time TimeVariable * CensorVariable(1);
  strata StrataVariable;
  test TreatmentVariable;
run;
```

Note that the interim efficacy analyses will be performed using R. For all interim and final analyses, the software used will calculate the log rank statistic using the formula in Section 8.1.1.

To perform a stratified Cox proportional hazards model for the final analysis and generate the treatment arm hazard ratio along with its confidence interval, the following pseudocode will be used. For any unstratified analyses, code can be used after the removal of the `strata ... ;` line and strata variable in the `class` statement.

```
proc phreg data=dataset;
  class StrataVariable(ref=StrataLabel)
  TreatmentVariable(ref=RemdesivirLabel);
  model TimeVariable * CensorVariable(1) = TreatmentVariable;
  strata StrataVariable;
  hazardratio TreatmentVariable / diff=ref cl=Wald;
  ods output HazardRatios = HRest;
run;
```

The following SAS pseudocode will be used to perform the final proportional odds model with treatment arm and disease severity as covariates and to generate the treatment odds ratio, p-value, and predicted probabilities of the ordinal scale levels by treatment arm and disease severity:

```
proc logistic data=dataset
  plots (only)=effect (x=ResponseVariable
    sliceby=DiseaseSeverityVariable*TreatmentVariable individual connect);
  class DiseaseSeverityVariable (param=ref ref=ModerateLabel)
    TreatmentVariable (param=ref ref=RemdesivirLabel);
  model ResponseVariable = TreatmentVariable StrataVariable;
  oddsratio TreatmentVariable;
  ods output OddsRatiosWald = ORest;
run;
```

6.2. Timing of Analyses

6.2.1. Early Sample Size Reassessment

A blinded estimate of the proportion of recoveries will be computed during the trial to evaluate whether the total sample size will provide the number of recoveries.

6.2.2. Interim analyses

A DSMB will monitor ongoing results to ensure patient well-being and safety as well as study integrity. The DSMB will be asked to recommend early termination or modification only when there is clear and substantial evidence of a treatment difference. More details about the interim analyses are described in Section 6.6.1 and Section 6.6.2 below as well as a separate guidance document for the DSMB. The summaries to be generated for the interim analysis are provided in the separate DSMB shell report.

6.2.3. Final Analyses

The final analyses of all outcomes and planned summaries/listings will be performed on the final full locked database and provided in the final report.

6.3. Analysis Populations

Summaries and analysis of safety data will be presented for the As Treated Population. Summaries and analysis of efficacy data will be presented for the intent-to-treat (ITT) population and As Treated population.

6.4. Covariates and Subgroups

Subgroup analyses for the main efficacy outcomes (i.e. the primary and key secondary analyses) will evaluate the treatment effect across the following subgroups:

- Geographic region:
 - US sites; Non-US sites
 - North American sites; Asian sites; European sites
- Duration of symptoms prior to enrollment
 - Quartiles
 - ≤ 10 days; > 10 days
 - \leq Median; $>$ Median
- Race (White; Black/African American; Asian; Other)
- Comorbidities
 - None; Any
 - None, One, Two or more
 - Obese; Non-Obese
- Age (<40 ; 40-64; 65 and older),
- Sex (Female; Male),
- Severity of disease
 - Randomization stratification: Moderate (ordinal 4/5); Severe (ordinal 6/7).
 - Actual disease severity at baseline: Moderate (ordinal 4/5); Severe (ordinal 6/7)
Note these analyses will only be performed if at least one subject is erroneously randomized into the incorrect disease severity stratum.
 - Baseline ordinal scale category: 4; 5; 6; 7

Additionally, main analyses of all secondary efficacy outcomes will evaluate the treatment effect across the following subgroups:

- Duration of symptoms prior to enrollment (\leq Median; $>$ Median)
- Severity of disease

- Randomization stratification: Moderate (ordinal 4/5); Severe (ordinal 6/7).
- Actual disease severity at baseline: Moderate (ordinal 4/5); Severe (ordinal 6/7)

Note these analyses will only be performed if at least one subject is erroneously randomized into the incorrect disease severity stratum.

- Baseline ordinal scale category: 4; 5; 6; 7

There will also be a sensitivity analysis of the primary, key secondary, and mortality outcomes to evaluate the effect of concomitant therapy including experimental treatment and off-label use of marketed medications that are intended as treatment for COVID-19 and are given to patient prior to and during the study. A blinded review of the concomitant medication data will be performed by the medical monitor to identify medications that fall into any of the following categories of “Medications of Interest”:

- Antivirals
 - Protease inhibitors
 - Polymerase inhibitors
- Potential Treatments for COVID-19
 - Hydroxychloroquine/Chloroquine
 - Other
- Corticosteroids
- Other anti-inflammatory drugs
 - Monoclonal Antibodies Targeting Cytokines
 - Other Biologic Therapies

Summaries of subjects who report use of the categories and subcategories of therapies/treatments will be provided. Note that after the blinded review of the medications, additional categories/sub-categories may be defined and/or categories/sub-categories may be combined.

In addition, the sensitivity analyses will consider the following categories (individually):

- Any Medication of Interest
- Hydroxychloroquine/Chloroquine
- Corticosteroids
- Other Anti-Inflammatory Drugs

For the recovery analyses, if a subject recovered prior to use of any of the medications/therapies, then the subject will still be counted as a recovery in the sensitivity analysis. For the analysis of the key secondary outcome, if a subject reports use of any of the medications/therapies prior to their Day 15 assessment, then the subject’s last clinical status score prior to medication/therapy use will be used as their Day 15 outcome. For the mortality analyses, subjects will be censored at the time of medication/therapy initiation.

In addition, the effect of treatment on the primary and key secondary efficacy outcomes will be explored via regression modeling controlling for age, duration of symptoms prior to enrollment, baseline d-dimer, and baseline CRP values as continuous covariates.

6.5. Missing Data

All attempts will be made to collect all data per protocol. Any data point that appears to be erroneous or inexplicable based on clinical judgment will be investigated as a possible outlier. If data points are identified as outliers, sensitivity analyses may be performed to examine the impact of including or excluding the outliers. Any substantive differences in these analyses will be reported.

For time to event outcomes, subjects who are lost to follow-up or terminate the study prior to Day 29 and prior to observing/experiencing the event will be censored at the time of their last observed assessment. Subjects who die prior to observing/experiencing the event will be censored at Day 29.

For the analysis of the key secondary outcome, subjects who are discharged but are subsequently re-admitted prior to Day 15 without a reported clinical score, their clinical score will be imputed at 7, which is the highest value for a hospitalized subject.

For the analyses of the secondary outcomes that involve clinical score (i.e. the key secondary outcome and time to improvement), if a subject is discharged from the hospital without a previously or concurrently reported clinical score of 1 or 2, then their clinical score at the time of discharge will be imputed as 2, which is the highest value for a non-hospitalized subject. If a subject terminates early from the study while they are hospitalized or completes the study while still hospitalized, the last observed clinical score assessment will be used as their final assessment.

For the modified version of the ordinal score described in Section 4.3, if a subject is discharged from the hospital without a previously or concurrently reported clinical score of 2 or 3, then their clinical score at the time of discharge will be imputed as 3, which is the highest value for a non-hospitalized subject.

For the analyses of the secondary outcomes described in Section 3.3, the following imputation rules will be used for subjects who are lost to follow-up, terminate early from the study, or do not have further outcome data available after discharge for any reason:

- Days of Non-invasive ventilation/high-flow oxygen:
 - If the subject's clinical status scale is 6 at the last observed assessment, then the subject will be considered to be on non-invasive ventilation/high-flow oxygen through Day 29. The endpoint will be total days when assessments are available plus all imputed days following the last observed assessment.
 - If the subject is not on non-invasive ventilation/high-flow oxygen at the last observed assessment, then the subject will be considered to not be on non-invasive ventilation/high-flow oxygen for the remainder of follow-up. Thus, no additional imputed days will be added to the number of days recorded on available assessments.

- Days of ventilation/ECMO:
 - If the subject's clinical status scale is 7 at the last observed assessment, then the subject will be considered to be on ventilation/ECMO through Day 29. The endpoint will be total days when assessments are available plus all imputed days following the last observed assessment.
 - If the subject is not on ventilation/ECMO at the last observed assessment, then the subject will be considered to not be on ventilation/ECMO through Day 29. Thus, no additional imputed days will be added to the number of days recorded on available assessments.
- Days of Oxygen:
 - If the subject's clinical status score is 5, 6, or 7 at the last observed assessment, then the subject will be considered to be on oxygen through Day 29. The endpoint will be total days when assessments are available plus all imputed days following the last observed assessment.
 - If the subject is not on oxygen at the last observed assessment, then the subject will be considered to not be on oxygen through Day 29. Thus, no additional imputed days will be added to the number of days recorded on available assessments.
- Days of Hospitalization
 - If the subject is discharged and no further hospitalization data are available, then the subject will be assumed to not have been readmitted. Thus, no additional imputed days will be added to the number of days recorded on available assessments. If a subject dies while hospitalized, the number of days of hospitalization will be imputed as 28 days.

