3.3.2. Recovery and Time to Recovery

The primary efficacy outcome measure is the time to recovery. Recovery will be defined as having a value of 1, 2, or 3 on the clinical status 8-point ordinal scale. The time to recovery will be defined as the elapsed time (in days) from randomization to the earliest day at which a subject

reaches recovery. Note that since clinical status assessments are recorded as defined in Section 4.3, the day that is being assessed (not necessarily the day the response is collected) will be used to determine the timing of events. For example, a subject with a score of 5 recorded on Days 1 - 3 and a score of 3 recorded on Day 4 will have a time to recovery equal to 3 days. It is also possible that a subject has a clinical status score > 3 reported for a particular day but was subsequently discharged on the same day. Such cases will be reviewed by the NIAID Medical Officer to make the determination of whether the subject should be considered recovered in analyses. Subject data to be reviewed as part of this determination will include the reported clinical status scores while hospitalized, where the subject was discharged to (e.g. private residence, rehabilitation facility, long-term care/nursing home), and any information regarding readmittance.

Any subjects that are lost to follow-up or terminated early prior to an observed recovery will be censored at the day of their last observed assessment. Subjects who complete follow-up but do not experience recovery will be censored at the day of their Day 29 visit. All deaths within Day 29 (and prior to recovery) will be considered censored at 28 days. Note that we do not expect many subjects to worsen after discharge.

However, we will evaluate whether any discharged subjects subsequently experience a worse clinical status and sensitivity analyses will be conducted accordingly. For these analyses, subjects who recover but are later re-admitted for COVID-19 will not be considered a recovery but will instead be censored at 28 days.

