3.3.4. Time to Clinical Status Improvement

Additional analyses will evaluate the time to improvement of at least one point on the clinical status 8-point ordinal scale. That is, improvement will be defined as a decrease of at least one point on the 8-point scale compared to the baseline value (e.g. from 5 to 4; from 5 to 3) and the time to improvement will be defined as the elapsed time (in days) from randomization to the earliest day of observed improvement. Note that since clinical status assessments are recorded as defined in Section 4.3, the day that is being assessed (not necessarily the day the response is collected) will be used to determine the timing of events.

For analyses of this outcome, imputation of the clinical score may be performed following the rules described in Section 6.5.

Any subjects that are lost to follow-up or terminated early prior to an observed improvement will be censored at the day of their last observed assessment. Subjects who complete follow-up but do

not experience improvement will be censored at the day of their Day 29 visit. All deaths within Day 29 (and prior to improvement) will be considered censored at 28 days.

An alternative definition of improvement will also be used where improvement will be defined as a decrease of at least two points on the 8-point scale compared to the baseline value (e.g. from 5 to 3; from 5 to 2). The timing and censoring definitions will follow similarly to the above.

3.3.5. Time to Discharge or NEWS of ≤ 2

The time to discharge or NEWS of ≤ 2 will be defined as the elapsed time (in days) from baseline to the earliest day at which either of the following occur:

- Discharge from hospital
- Reported NEWS of ≤ 2 which is maintained for 24 hours

For the latter bullet, to meet this criterion, scores of ≤ 2 must be reported on consecutive study visits. The timing of the event will be set to the day of the second assessment.

All deaths that occur before discharge or before an observed NEWS of ≤ 2 will be considered censored at 28 days.

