- Figures displaying time to recovery Kaplan-Meier curves within subgroups defined by baseline ordinal score were added to match the figures generated for ACTT-1.

Figure 12:

- Forest plot of the hazard ratios of time to recovery by comorbidity was added to match the figure generated for ACTT-1.

Figure 17, Figure 18, Figure 19, Figure 20, Figure 21, Figure 22, Figure 23, Figure 24:

- Figures displaying time to improvement Kaplan-Meier curves within subgroups defined by baseline ordinal score were added to match the figures generated for ACTT-1.

Figure 28, Figure 29, Figure 30, Figure 31:

- Figures displaying time to discharge or NEWS ≤ 2 Kaplan-Meier curves within subgroups defined by baseline ordinal score were added to match the figures generated for ACTT-1.

Figure 44 and Figure 46:

- Figures displaying time to death Kaplan-Meier curves within subgroups defined by disease severity and baseline ordinal score were added to match the figures generated for ACTT-1.

Figure 47, Figure 48, Figure 49, Figure 50:

- Figure displaying time to death Kaplan-Meier curves within subgroups defined by disease severity was added.

The below summarizes the changes made to the SAP from version 1.0 to version 2.0:

Throughout the document:

- Typos and errors introduced via copying/pasting language from other sections were corrected.

Section 3.3.2:

- Language was added to the definition of recovery to note that subjects who are discharged to another hospital, hospice, or similar health care institution will not be considered recovered.

Section 6.4:

- The Prohibited Medications that are being explored in sensitivity analyses were renamed “Medications of Interest”. Corresponding tables and listings were updated accordingly.

Section 6.5:

- Language was added to the imputation rules for clinical scores to note that if a subject terminates early from the study while they are hospitalized or completes the study while still hospitalized without a reported clinical score on the day of discharge, the last observed clinical score assessment will be used as their final assessment.

Section 9.4:

- A supplemental analysis of the time to death outcome was added to explore the interaction between treatment and baseline disease severity with respect to the effect of treatment on the outcome.

Appendices:

- Multiple tables and listings were updated to fix omissions/errors and provide additional programming notes.

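### SAP 6.5 and 3.3.5 credit a hospital discharge as improvement without looking at destination, so a transfer or inpatient hospice placement recorded as a discharge becomes a false event in time to improvement and in time to discharge or NEWS ≤ 2

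*SAP*

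**What the plan says.** SAP 6.5 limits the scope of the rule: "For the analyses of the secondary outcomes that involve clinical score (i.e. the key secondary outcome and time to improvement". The trigger is "if a subject is discharged from the hospital without a previously or concurrently reported clinical score of 1 or 2", and the consequence is "then their clinical score at the time of discharge will be imputed as 2, which is the highest value for a non-hospitalized subject". Destination and level of support play no part.

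SAP 3.3.4 takes the earliest day of improvement. For the two-category version, "improvement will be defined as a decrease of at least two points on the 8-point scale compared to the baseline value". SAP 3.3.5 lists "Discharge from hospital" as one of two qualifying events, without a condition.

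The primary endpoint is handled differently. Under SAP 3.3.2, a subject scored above 3 on a day and discharged that same day goes to the sponsor's Medical Officer, who decides whether this is a recovery. The information reviewed includes "where the subject was discharged to (e.g. private residence, rehabilitation facility, long-term care/nursing home" and readmission.

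Two other rules in SAP 6.5 touch the same subject. If the last observed score is 7 and no further data exist after discharge, ventilation/ECMO is assumed to continue through Day 29. For hospital days, a discharged subject without further data is assumed not readmitted, and "If a subject dies while hospitalized, the number of days of hospitalization will be imputed as 28 days".

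The current text does not define discharge. The SAP's change log (Section 15), read here only for vocabulary, says that "subjects who are discharged to another hospital, hospice, or similar health care institution will not be considered recovered".

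**The concern.** Score 2 is a cautious choice for someone who has gone home, because it is the worse of the two non-hospitalized categories. It is not cautious for someone moved to another hospital, who is still hospitalized.

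The trigger is not unusual. Under Protocol Appendix B, 8.1.2.2, scores are taken daily only in hospital and then on Days 15, 22 and 29, and each reports the worst state of the previous day. Few subjects will have a 1 or 2 on record when they first leave, so the rule probably governs most first discharges. Most of those are genuine. The concern is the minority who leave because they are worse.

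For them, a bad outcome is scored near the best end of the scale. Because time to improvement takes the first qualifying day, a later death does not undo the event. One subject could be not recovered in the primary, ventilated through Day 29 in the ventilator-day summary, and improved by five categories in time to improvement.

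**Working it through.** **The plan's own figures.** The primary event count is E = 4(1.96 + z_β)²/{ln θ}². With z_β = 1.0364 and θ = 1.25, E = 4 × 8.979/0.04979 = 721.3, or 722 rounded up, against 723 stated. 723/0.70 = 1032.9, against 1032 stated. The key-secondary formula (scenario 1, odds ratio 1.75) gives 394, against 396 stated. All reproduce closely, and none changes, because the point concerns endpoint derivation.

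**Score arithmetic.** Baseline scores run from 4 to 7 (SAP 6.4). Improvement is baseline minus 2:

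| Baseline | Imputed 2: points gained | One category? | Two categories? |
|---|---|---|---|
| 4 | 2 | yes | yes |
| 5 | 3 | yes | yes |
| 6 | 4 | yes | yes |
| 7 | 5 | yes | yes |

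The imputed score therefore always meets both definitions. On the modified scale of SAP 4.3 the imputed score is 3, and only a baseline of 4 then falls short of two categories (a gain of 1).

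**One subject under each rule.** Score 7, recorded as discharged to another hospital, no later data:
- Time to improvement (3.3.4 with 6.5): event on both definitions.
- Time to discharge or NEWS ≤ 2 (3.3.5): event.
- Hospital days (6.5): no further days added.
- Ventilator/ECMO days (6.5): ventilated through Day 29.
- Primary (3.3.2): Medical Officer review, including destination.

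**Size for time to improvement.** The documents give no transfer or hospice rate, so 0.5% to 5% of 1032 is assumed. That is k ≈ 5 to 52 false events. For illustration, borrow the primary's 723 events and ratio of 1.25, and let the false events carry no treatment effect. The diluted ratio is exp{723 × ln 1.25/(723 + k)}:
- k = 5: 1.248, with power 84.8% against 85.1% before.
- k = 52: 1.231, with power 82.6%.

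If instead all the excess fell in one arm (0.5% to 5% of that arm, no true effect, 70% event share), the apparent ratio would be about ln(1 − 0.70 − d)/ln(0.30). That is 1.01 at d = 0.005 and 1.15 at d = 0.05, in favour of whichever arm had more such discharges.

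**Size for Day 15 status.** Take scenario 5 (Protocol Appendix B, Table 6) and an odds ratio of 1.25. Categories 7 and 8 hold 6.0% of control. The treated odds are (0.06/0.94)/1.25 = 0.0511, which is 4.9%. Assume affected subjects are half 7 and half 8, all moved to 2, at rates proportional to those shares. Refitting the proportional odds model to the expected proportions gives:

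| Control affected | Fitted OR | Fitted OR if deaths stay at 8 |
|---|---|---|
| 1% | 1.242 | 1.246 |
| 2% | 1.234 | 1.242 |
| 3% | 1.227 | 1.238 |

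Under a true odds ratio of 1.00 the two arms have equal shares, and the fitted value is exactly 1.00.

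**The case against.** The strongest reply is that a transfer may not be a discharge at all. The exclusion criterion in Protocol Appendix B, 5.2 names anticipated discharge and anticipated transfer to a non-study hospital as separate events. SAP 6.5 also uses the last observed score for a subject who terminates early while hospitalized, which is close to the carry-forward a transfer needs. This stands in part: the current text is open. Only the change log speaks of being discharged to another hospital or hospice. The point is therefore conditional on how sites record these cases.

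Second, Day 15 status is largely protected. SAP 3.3.3 uses the score collected at the Day 15 visit. Discharged subjects can be reached by phone for status, readmission and mortality (Appendix B, 1.2). Readmission before Day 15 without a score is imputed as 7 (SAP 6.5). An ordinal assessment is required the day after a death (Appendix B, 8.1.2.2), and SAP Table 33 counts death at or before the visit as 8. This stands.

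Third, a reader might infer that every discharge is scored 2. It is not: a reported 1 or 2 is kept.

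Fourth, a reader might infer bias against the better arm, on the ground that such discharges are commoner in the arm doing worse. Assuming a 2:1 split between arms, the Day 15 odds ratio of 1.25 would become 1.22, 1.20 and 1.18 (1% to 3% of control affected), and a true 1.00 would become 0.98, 0.96 and 0.93. The documents give no rates and no imbalance. Scenario 5 itself implies about 1.23:1, and the shift under the null comes entirely from the assumed imbalance. Those figures also score as 2 patients who have died, contrary to the provisions above.

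Finally, the primary endpoint is untouched, secondary analyses carry no multiplicity adjustment (SAP 6.8), and SAP 2.1 leaves some imputation detail to a manufacturer's addendum that is not among these documents. All of this limits the consequence. None of it supplies a destination rule for the analyses in this SAP.

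**Conclusion.** The point holds conditionally. Where a hospital transfer or inpatient hospice placement is recorded as a discharge, SAP 6.5 and 3.3.5 turn a bad outcome into a favourable event, and the plan's own rules then contradict each other for the same subject. The effect is direct and irreversible for time to improvement and for time to discharge or NEWS ≤ 2. It is small for Day 15 status.

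Direction and size cannot be determined from the documents; the rates above are assumptions. The exclusion of transfers anticipated within 72 hours lowers the number of cases but does not remove later ones. Nor does SAP 3.3.2 give the primary a fixed rule for hospital or hospice destinations; its protection is case-by-case review. Home hospice is a separate case, since it literally meets category 2. The change is worth making because it is cheap and removes a visible inconsistency, not because a large bias has been shown.

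**What to change.** - Define discharge in the SAP as leaving for a non-acute setting.
- Extend the destination review of SAP 3.3.2 to 6.5 and 3.3.5, and state that it is done blind to treatment arm; 3.3.2 does not say so now.
- Impute 2, and count a discharge event, only when the subject is no longer hospitalized.
- For transfer to another acute hospital or inpatient hospice, carry the last inpatient score forward until a later score or death is recorded. Count no improvement or discharge event, and keep counting hospital days.
- Handle home hospice in a sensitivity analysis that does not count it as improvement.

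The cost is SAP wording and some derivation work, using destination information the sponsor already reviews for the primary. There will be slightly fewer improvement and discharge events. No sample-size figure changes.
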